6.4. Handling of Missing Data

For a given subject and a given efficacy/immunogenicity measurement, missing measurements will not be replaced. Therefore, an analysis will exclude subjects with missing values.

For the analysis of solicited symptoms, systemic reactions and respiratory illness symptoms, missing or non-evaluable measurements will not be replaced. Therefore the analysis of the solicited symptoms based on the Safety cohort will include only subjects/doses with documented safety data.

There is no imputation in cases where severity or relationship information is missing for AEs.

6.5. Handling of Missing or Incomplete Dates

6.5.1. Missing or Partial AE Start Date

If only Day of AE start date is missing:

If the AE start year and month are the same as that for the first vaccination dose date, then:

- If the full (or partial) AE end date is NOT before the first dose date or AE end date is missing, then impute the AE start day as the day of first dose date; otherwise, impute the AE start day as 1.
- Otherwise, impute the AE start day as 1.

Sponsor: Medicago; Protocol No.: CP-PRO-QVLP-014

Compare the imputed AE start date with the vaccination date to determine whether the AE is medical history or treatment emergent adverse event (TEAE).

If Day and Month of AE start date are missing:

If AE start year = first dose year, then:

• If the full (or partial) AE end date is NOT before the first dose date or AE end date is missing, then impute the AE start Month and Day as the Month and Day of first dose date; otherwise, impute the AE start Month as January and the Day as 1.

Compare the imputed AE start date with the vaccination date to determine whether the AE is medical history or TEAE.

If Year of AE start date is missing:

If the year of AE start is missing or AE start date is completely missing then query site with no imputation. Also compare the full (or partial) AE end date to the first dose date. If the AE end date is before the first dose date then the AE should be considered as a medical history. Otherwise, the AE will be considered as TEAE.

6.5.2. Missing or Partial Concomitant Medication Start/Stop Dates

Missing or partial concomitant medication start date:

- If only DAY is missing, use the first day of the month.
- If DAY and Month are both missing, use the first day of the year.

Missing or partial concomitant medication stop date:

- If only DAY is missing, use the last day of the month.
- If DAY and Month are both missing, use the last day of the year.
- If DAY, Month and year are all missing, assign 'continuing' status to stop date.

6.6. Visit Windows

The collected data will be summarized by scheduled visits based on the scheduled events indicated in Table 1. The visits indicated on the electronic Case Report Form (eCRF) will be used as the analysis visits.

6.7. Pooling of Centers

No center pooling will be employed.

6.8. Subgroups

The subgroup analysis by age stratum will be performed for all the endpoints as applicable.

7. DEMOGRAPHIC, OTHER BASELINE CHARACTERISTICS AND MEDICATION

7.1. Subject Disposition and Withdrawals

All subjects who provide informed consent will be accounted for in this study. Subject disposition information will be summarized by treatment group and overall. Screened subjects will be presented for the overall population. The frequencies and percentages of subjects who are vaccinated in each analysis set, completed through day 21, completed the study and early study withdrawals along with primary reasons for withdrawal will be presented. The same information will be repeated for the immunogenicity subset.

The number of subjects vaccinated will be used as the denominator for the percentage calculation.

Subject disposition will be listed.

In addition, a listing will be provided to include population sets, completion of the study and withdrawal information by subject and age stratum.

Screen failures will also be listed with reason for not being randomized.

7.2. Demographic and Baseline Characteristics

7.2.1. Demographics

Age, height, weight and BMI at baseline will be summarized descriptively. Age category (65-74 years and >75 years), sex, race, ethnicity, influenza immunization history, and coexisting conditions will be summarized using the SAS, PP and IPP.

The same information will be listed by subject and age stratum.

7.2.2. Baseline and Disease Characteristics

Continuous baseline variables such as OT (°C), systolic BP (mmHg), diastolic BP (mmHg), and HR (beats/min) will be summarized by descriptive statistics in the same way as continuous demographic variables for the SAS, PP and IPP subset.

7.2.3. Protocol Deviations

The protocol deviations by category will be summarized by treatment group and overall. Population membership details will be listed, including reason for exclusion from each population (on randomized patients).

A listing will include the protocol deviations identified based on data recorded on the eCRF and/or protocol deviation logs (on randomized patients) and presented along with the date the deviation occurred relative to study day, and deviation category.

7.2.4. Medical History

The frequencies and percentages of subjects with medical history findings will be presented by system organ class (SOC) using the Medical Dictionary for Regulatory Affairs (MedDRA®)

Version 21.0 or higher by treatment group and overall. Medical history data will be tabulated for the SAS following the order mentioned in Appendix A.

The details of medical history findings will be listed by subject and age stratum.

In addition, another listing will be added to include details of influenza immunization history by subject and age stratum

7.2.5. Prior and Concomitant Medication

Medications used in this study will be coded by using the World Health Organization Drug Dictionary Enhanced (WHO DDE) + Herbal, March 2018.

Prior medications are medications used only before the first study vaccination (medication end date < first study vaccination date).

Concomitant medications are defined as those medications with a start date on or after the vaccination dose of study drug or the medications started before the dose and continued on or after the vaccination.

Prior medications and concomitant medications will be summarized descriptively using frequency tables by Anatomical Therapeutic Chemical (ATC) class (ATC Level 1) and preferred term (PT) (or ATC Level 3) by treatment group. Details for imputing missing or partial start and/or stop dates of medication are described in Section 6.5.2.

In addition, prior medications and concomitant medications will be listed with ATC classification and preferred term (or ATC Level 3) by subject and age stratum.

7.2.6. Treatment Exposure

Since the subjects will receive only one dose of study vaccination, duration will not be calculated. An individual listing will be provided to include details of vaccine administration by subject and age stratum.

7.2.6.1. Treatment Duration

Since the subjects will receive only one dose of study vaccination, duration will not be calculated.

7.2.6.2. Treatment Compliance

Treatment compliance is expected to be 100%, since the study treatments will be administered IM at each Investigator site by site staff. In addition, the Investigator or designated study center personnel will maintain a log of all study treatments dispensed and returned during the study.

Compliance information will not be summarized.

8. EFFICACY

8.1. Efficacy Evaluation

Following randomization and vaccination, subjects will be instructed to report respiratory symptoms and symptoms meeting the definition of ILI from Day 14 until the end of the surveillance period (passive surveillance). The subjects will be given a memory aid listing the symptoms of respiratory illness and ILI and contact information for the study site. During this same period, active surveillance will also be performed to solicit respiratory illness symptoms a minimum of once per week:

- North America and Europe: Prior to the start of the influenza season (the start of influenza season will be determined by Medicago through local epidemiology and clinical experience), subjects will be contacted at least once per week, using the contact method most likely to be successful (e.g. subject's preferred method [phone, text, e-mail]). During the influenza season, subjects will be contacted a minimum of two times per week; at least one of these weekly contacts will be through a scripted telephone call, with the remaining contacts via the method most likely to be successful;
- Asia: Since there generally is no clearly defined influenza season, contacts will be made a minimum of two times per week, with at least one of these weekly contacts through a scripted telephone call and the remaining contacts via the method most likely to be successful (e.g. subject's preferred method [phone, text, e-mail]).

A respiratory illness will be defined as the occurrence of a new onset of one or more of the following symptoms that persist(s) for or reoccur(s) after a period of at least 12 hours:

- Sneezing;
- Stuffy or runny nose (nasal congestion);
- Sore throat:
- Cough;
- Sputum production;
- Wheezing;
- Difficulty breathing.

An episode is considered to extend from the first day of the first symptom to the last day of the last symptom. In most instances a new episode can only begin after resolution of all symptoms of the previous episode, with a separation of a seven-day symptom-free interval between episodes.

Within 36 hours (preferably within 24 hours) after the reporting of a respiratory illness, the clinic site will collect NP swabs from the subject (two per subject per event) if the start of the respiratory illness falls in the indicated regional timeframe:

- North America and Europe: after the start of influenza season;
- Asia: after the start of active and passive surveillance (Day 14 and onwards).

The swabs must be collected prior to the use of any influenza antiviral treatment medication (e.g. oseltamivir, zanamivir, rapivab). If the respiratory illness starts prior to Day 14, swabs are not to be collected, even if symptoms persist beyond Day 14.

A swab will be submitted for analysis by multiplex RT-PCR. In the event of a positive RT-PCR result (positive for A or B strains), additional testing will be done to attempt to isolate the virus or for additional cell-culture testing (typing, subtyping, and strain identification and genetic sequencing using HI assay against a panel of known standard ferret reference antisera to different viral strains) to determine if the virus detected is matched or similar to any of the strains covered in the vaccine formulation for the respective season. A positive RT-PCR result will be considered a laboratory-confirmed case of influenza. The NP swabs will be analyzed in a central laboratory; information on processing and the central laboratories will be provided in the study-specific documentation.

Any respiratory illness must be followed up for 30 days following the start date; this follow up will be conducted via the planned active surveillance contacts (telephone and text messaging), using a script. At the end of the 30-day follow up, a questionnaire regarding disease burden due to the respiratory illness will be completed; subjects will be provided with a memory aid for use over the 30 days, to facilitate accurate reporting at the end of the follow-up period.

ILI will also be monitored during this study. A subject will be considered to have protocoldefined ILI if the following two conditions are both met between Day 14 and the end of the surveillance period:

- He/she has at least one of the following pre-defined respiratory symptoms:
 - Sore throat;
 - Cough;
 - Sputum production;
 - Wheezing; or
 - Difficulty breathing;

AND

- He/she has at least one of the following systemic symptoms:
 - Fever (defined as a temperature > 37.2 °C or > 99.0 °F);
 - Chills;
 - Tiredness;
 - Headache; or
 - Myalgia.

In addition, information on the following uncommon ILI symptoms will be collected for any subjects with a protocol-defined respiratory illness during the surveillance period: nausea, vomiting, and diarrhea.

8.2. Analysis of Primary Efficacy Endpoint

The primary efficacy endpoint defined in Section 4.1.1 will be analyzed using the PP set as outlined below:

For the primary endpoint, VE will be evaluated as the relative risk of subjects vaccinated with Quadrivalent VLP Influenza Vaccine (30 μ g/strain) or an active comparator to develop protocoldefined ILI as a result of laboratory-confirmed infection with any influenza virus (RT-PCR) \geq 14 days after vaccination.

VE will be calculated using the following formula:

$$VE=(1-RR)=(1-ARV_V/ARV_C)*100 \%$$

Where:

RR = relative risk

 ARV_V = attack rate in subjects vaccinated with the Quadrivalent VLP Influenza Vaccine; and

ARV_C = attack rate in subjects vaccinated with an active comparator.

Non-inferiority will be concluded if the lower limit of the two-sided 95 % CI for relative VE is > -20 % for the primary endpoint. If non-inferiority is demonstrated, VE of the VLP vaccine will be tested for superiority over the active comparator as an exploratory analysis (VE for superiority testing will use the same definitions as in the primary endpoint). Superiority will be concluded if the lower limit of the two-sided 95 % CI for relative VE is > 9 % for the primary endpoint.

The primary endpoint will be summarized descriptively with VE and its 95% CI.

The analyses of the primary efficacy endpoint will be repeated for the FAS.

8.2.1. Multiplicity

Multiplicity adjustment will not be done for the primary endpoint because there is only one.

8.2.2. Methodology for Computing CI

8.2.2.1. Wilson Score 95% CIs

The 95% CI around RR will be calculated based on score confidence limits.

SAS® Code [4, Orenstein 1985]:

```
Proc freq data= ADZ (with the appropriate analysis dataset);
table group*resp/relrisk (cl=SCORE) ;
run;
```

Note: 95% Lower Confidence Limit for VE = 1-95% Upper Score Confidence Limit.

8.3. Analysis of Secondary Efficacy Endpoints

The secondary efficacy endpoints which are defined in Section 4.1.2 will be analyzed in the following manner:

VE and 95% CI will be calculated for the secondary efficacy endpoints using the same formula indicated for the primary efficacy analysis.

For secondary efficacy endpoints, the sub-analyses (VE and its 95% CI) by each strain (homologous A/Michigan/45/2015 [H1N1], homologous A/Singapore/INFIMH-16-0019/2016 [H3N2], homologous B/Colorado/06/2017 and homologous B/Phuket/3073/2013), where applicable, and by age group (65-74 and >75) will be summarized.

Non-inferiority will be tested using the same criterion as with the primary endpoint; superiority testing will be conducted if non-inferiority is concluded (the same criterion as with the primary endpoint will be used for superiority testing).

All the secondary efficacy analyses will be based on the PP and will be repeated for the FAS as well.

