3.2. Secondary Objectives

Efficacy:

- To evaluate the efficacy, relative to an active comparator, of a single 30 μg/strain dose
 of the Quadrivalent VLP Influenza Vaccine, against laboratory-confirmed protocoldefined influenza-like illness (ILI) caused by vaccine-matched strains (sequential RTPCR & serotyping);
- To evaluate the efficacy, relative to an active comparator, of a single 30 μg/strain dose
 of the Quadrivalent VLP Influenza Vaccine, against laboratory-confirmed protocoldefined respiratory illness caused by vaccine-matched strains (sequential RT-PCR &
 serotyping);
- 3. To evaluate the efficacy, relative to an active comparator, of a single 30 μg/strain dose of the Quadrivalent VLP Influenza Vaccine, against laboratory-confirmed protocoldefined respiratory illness caused by any influenza viral types/subtypes (matched, mismatched, and un-typed) (sequential RT-PCR);
- 4. To evaluate the efficacy, relative to an active comparator, of a single 30 μ g/strain dose of the Quadrivalent VLP Influenza Vaccine, as measured by the incidence of subjects presenting with symptoms of protocol-defined ILI, regardless of laboratory results.
- 5. To evaluate the efficacy, relative to an active comparator, of a single 30 μg/strain dose of the Quadrivalent VLP Influenza Vaccine, against laboratory-confirmed protocoldefined influenza-like illness (ILI) caused by any influenza viral types/subtypes (matched, mismatched, and un-typed) (sequential RT-PCR) according to prior exposure to influenza vaccines;

Safety:

1. To assess the safety and tolerability, relative to an active comparator, of a single $30 \mu g/strain$ dose of the Quadrivalent VLP Influenza Vaccine.

Immunogenicity:

 To assess, in a subset of 420 subjects (210 subjects per treatment group), the immunogenicity of a single 30 μg/strain dose of Quadrivalent VLP Influenza Vaccine and an active comparator, as measured by Hemagglutination Inhibition (HI) assay, Microneutralization (MN) assay, and Single Radial Hemolysis (SRH) assay against homologous and heterologous (HI only) influenza strains.

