3.3. Exploratory Objectives

Efficacy:

- To evaluate the efficacy, relative to an active comparator, of a single 30 μg/strain dose
 of the Quadrivalent VLP Influenza Vaccine, against protocol-defined respiratory illness
 due to mismatched influenza strains (sequential RT-PCR & serotyping);
- To determine the efficacy, relative to an active comparator, of a single 30 μg/strain dose
 of the Quadrivalent VLP Influenza Vaccine, as measured by the incidence of subjects
 presenting with symptoms of protocol-defined respiratory illness, regardless of
 laboratory results.
- 3. To evaluate whether or not vaccine efficacy (VE) is maintained (no waning) through time after vaccination for the primary efficacy endpoint, that is, protocol-defined ILI caused by any influenza viral type/subtype.

Safety:

1. To evaluate respiratory illness outcome, occurrences of pneumonia, new onset or exacerbations of cardio-respiratory conditions, and health care utilization of subjects administered the Quadrivalent VLP Influenza Vaccine at a dose of 30 μg/strain relative to subjects administered an active comparator.

Immunogenicity:

[figure not shown]
1. To assess the Cell-Mediated Immune (CMI) response against homologous strains of a single 30 μg/strain dose of Quadrivalent VLP Influenza Vaccine and an active comparator on Days 0 and 21 in a subset of 420 subjects (same subset as the immunogenicity subset; 210 subjects per treatment group).

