Reports of respiratory illness will be followed up for the collection of information regarding symptoms, concomitant medication use, and disease burden and the collection of two nasopharyngeal (NP) swabs. For subjects in North America and Europe, swabs will only be collected for cases of respiratory illness that occur after the start of the influenza season (as determined by Medicago through local epidemiology and clinical experience); for subjects in Asia, swabs will be collected for any cases of respiratory illness reported during the surveillance period (Day 14 and onwards). Figure 2 outlines the process to be followed for reports of respiratory illness.

^{*} One or more of the following symptoms that persist(s) for or reoccur(s) after a period of at least 12 hours: sneezing, stuffy or runny nose (nasal congestion), sore throat, cough, sputum production, wheezing, and difficulty breathing

Figure 2 Flowchart of Process of Respiratory Illness Report

Throughout the influenza season, the number of laboratory-confirmed influenza cases will be reviewed periodically by selected members of Medicago and the CRO who will be independent of study conduct and analysis. In the event of an insufficient attack rate of confirmed influenza (minimum of 198 cases), the study will be either continued or extended into another season to enroll more subjects and a protocol amendment will be issued to address changes to the enrolment plan.

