4.1.2. Secondary Endpoints

- 1. Occurrences of laboratory-confirmed influenza illnesses (according to protocol defined ILI; ≥ 14 days post-vaccination) caused by influenza viral types/subtypes that are matched (and/or antigenically similar) to the strains covered in the vaccine formulation (sequential RT-PCR & serotyping);
- 2. Occurrences of laboratory-confirmed influenza illnesses (according to protocol defined respiratory illness; ≥ 14 days post-vaccination) caused by influenza viral types/subtypes that are matched (and/or antigenically similar) to the strains covered in the vaccine formulation (sequential RT-PCR & serotyping);
- 3. Occurrences of laboratory-confirmed influenza illnesses (according to protocol defined respiratory illness; ≥ 14 days post-vaccination) caused by any influenza viral types/subtypes (matched, mismatched, and un-typed) (sequential RT-PCR);
- 4. Occurrences of protocol-defined ILI ≥ 14 days post-vaccination (confirmed or not by laboratory testing).
- 5. Occurrences of laboratory-confirmed influenza illnesses (according to protocol defined ILI; ≥ 14 days post-vaccination) caused by any influenza viral types/subtypes (matched, mismatched, and un-typed) according to prior exposure to influenza vaccines.

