4.1.3. Exploratory Endpoints

- 1. Occurrences of laboratory-confirmed influenza illnesses (according to protocol defined respiratory illness; ≥ 14 days post-vaccination) caused by mismatched influenza viral strains (sequential RT-PCR & serotyping);
- 2. Occurrences of respiratory illnesses \geq 14 days post-vaccination (confirmed or not by laboratory testing).
- 3. The slope estimate of the weighted Schoenfeld residuals against event time based on the Cox proportional hazard model for the primary endpoint, that is, protocol-defined ILI caused by any influenza viral type/subtype.

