8.4. Analysis of Exploratory Endpoints

The exploratory efficacy endpoints 1 and 2 which are defined in Section 4.1.3 will be analyzed using the same formula indicated for the primary efficacy analysis. The sub-analyses (VE and its 95% CI) by age group will be summarized.

Non-inferiority will be tested using the same criterion as with the primary endpoint; superiority testing will be conducted if non-inferiority is concluded (the same criterion as with the primary endpoint will be used for superiority testing).

Summaries of study outcomes for those with 'respiratory illness' or systemic illness (ILI) will be presented for the overall population as well as by age and treatment group.

In addition, an individual listing will be included to present details of the results of RT-PCR and typing (laboratory-confirmed influenza vaccine matched, mismatched strains, or un-typed strains), respiratory illness symptoms, and ILI by subject and age stratum.

For the exploratory efficacy endpoint 3 defined in Section 4.1.3, the presence of VE waning can be tested by the linear trend (i.e., the proportional hazards) in the scaled Schoenfeld residuals from the Cox proportional hazard model [Petrie 2016, Durham 1998]. Specifically, it will be analyzed as below:

Step 1: Fit a regular Cox proportional hazard model with the treatment group as the main effect, and Fluarix will be coded as the reference group in the model.

Step 2: Find the scaled Schoenfeld residual from the Cox proportional hazard model in step 1. The scaled Schoenfeld residual has value at all event-time for the main effect (treatment group);

Sample SAS® Code:

```
Proc phreg data = ADZ (with the appropriate analysis dataset);
model AVAL*Censor(1) = TRTP / (ref = `Fluarix');
output out=res wtressch = TRTP_r;
run;
Note: Censor indicates censoring status: 1 = Censored; 0 = protocol-defined ILI due to laboratory-confirmed influenza.
```

Step 3: Fit a linear regression on the scaled Schoenfeld residuals against event time.

Sample SAS® Code:

```
Proc GLM data = res;
model TRTP_r = AVAL;
  ods output ParameterEstimates= prms;
run;
Note: AVAL in step 2 and 3 is the event time for the primary efficacy endpoint, protocol-defined ILI caused by any influenza viral type/subtype.
```

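### The -20% non-inferiority rule set for RT-PCR-confirmed ILI is carried unchanged to ILI and respiratory illness counted with or without confirmation, where the 1.2 margin can exceed the comparator's whole effect

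*SAP*

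**What the plan says.** The primary rule is in SAP 8.2 and protocol 12.3.1: non-inferiority is concluded if the lower limit of the two-sided 95% CI for relative VE exceeds -20%, and superiority (exploratory) if it exceeds 9%. SAP 3.6 sizes the trial on that rule for ILI due to influenza, with 2% or more in the comparator arm, 20% relative VE and 10% dropout.

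SAP 8.3 carries the rule to all secondary efficacy endpoints: "Non-inferiority will be tested using the same criterion as with the primary endpoint; superiority testing will be conducted if non-inferiority is concluded". SAP 8.4 repeats it for exploratory endpoints 1 and 2: "Non-inferiority will be tested using the same criterion as with the primary endpoint". Protocol 12.3.2 and 12.3.3 agree.

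Two of these endpoints are not influenza-specific:

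- Secondary endpoint 4 (SAP 4.1.2): "Occurrences of protocol-defined ILI ≥ 14 days post-vaccination", whether or not a laboratory confirms it. The matching objective in SAP 3.2 is efficacy "as measured by the incidence of subjects presenting with symptoms of protocol-defined ILI, regardless of laboratory results".
- Exploratory endpoint 2 (SAP 4.1.3): respiratory illness on the same basis. Its objective in SAP 3.3 begins "To determine the efficacy, relative to an active comparator".

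Under SAP 8.1, ILI needs one respiratory and one systemic symptom, for example cough and tiredness, and counts if "the following two conditions are both met between Day 14" and the end of surveillance. Respiratory illness needs one symptom, such as sneezing. In North America and Europe, "swabs will only be collected for cases of respiratory illness that occur after the start of the influenza season" (SAP 3.4). These regions are 12 of 13 parts of the planned 8:4:1 sample (SAP 3.7.1). Protocol 4.2.7 explains that swabs before the season would add little.

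**The concern.** The two endpoints count illness that the plan itself expects to be largely unrelated to influenza, including pre-season illness that is not swabbed in most of the sample. If that illness is equally common in both arms, it moves the risk ratio towards 1 whatever the vaccine does against influenza. A fixed margin of 1.2 then becomes easier to meet as the influenza share falls, and a conclusion presented under an efficacy objective says less about efficacy.

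Neither document justifies the margin for these endpoints, or gives an expected total illness rate or influenza share. No text makes these tests depend on the primary result. What is at stake is the meaning of a non-inferiority statement on all-cause illness, above all if the primary has failed.

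**Working it through.** **Plan's own figure.** Comparator rate 0.020, test rate 0.016, margin 1.2, one-sided 0.025, 80% power. With the unpooled statistic pT - 1.2pC:

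n = (1.96 + 0.8416)² × (0.016×0.984 + 1.44×0.020×0.980) / (0.016 - 0.024)² ≈ 5,393 per arm.

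Dividing by 0.9 gives 5,993 per arm, or 11,986 in total, against 12,120 stated (1.1% apart). At 6,060 × 0.9 = 5,454 evaluable per arm, log-RR power is 81% and expected cases are 5,454 × 0.036 = 196, against the plan's minimum of 198. The design reproduces for the confirmed endpoint.

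**Model for all-cause illness.** Let f be the influenza rate and q the total illness rate in the comparator arm, with non-influenza illness equal in both arms (an assumption). Then

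- p0 = q and p1 = q + f(RRflu - 1);
- with influenza share s = f/q, an all-cause RR of 1.2 equals an influenza RR of 1 + 0.2/s. At f = 2% and q = 10%, s = 0.2 and this is 2.0;
- an inert vaccine has RRflu = 1/(1 - VE), where VE is the comparator's efficacy against no vaccine;
- the margin exceeds the comparator's whole effect once q > 5f(1/(1 - VE) - 1).

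Break-even total ILI for VE 27/40/50%: 3.7/6.7/10% at f = 2%, and 7.4/13.3/20% at f = 4%.

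**Inputs.** f = 2% is the planning floor in SAP 3.6. The 4% rows also stand for 2% confirmed with half of influenza ILI missed. VE 27% is the 2012-2013 figure for people aged 65 and over in the protocol Introduction; 40% and 50% are assumed, as are all values of q.

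**Chance that an inert vaccine meets the rule**, n = 5,454 per arm:

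P = Φ[(ln 1.2 - ln(p1/p0))/SE - 1.96], SE = √[(1-p0)/(n p0) + (1-p1)/(n p1)].

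Example: f = 2%, VE 27%, q = 10%. p1 = 0.10 + 0.02 × 0.370 = 0.1074, RR 1.074, SE 0.0563, so P = Φ(1.97 - 1.96) = 0.50.

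| Influenza rate | Comparator VE | ILI 5% | 10% | 15% | 20% |
|---|---|---|---|---|---|
| 2% | 27% | 8% | 50% | 85% | 97% |
| 2% | 40% | 0.4% | 18% | 59% | 88% |
| 2% | 50% | 0% | 2.5% | 25% | 65% |
| 4% | 27% | 0.2% | 12% | 51% | 84% |
| 4% | 40% | 0% | 0.15% | 6% | 34% |
| 4% | 50% | 0% | 0% | 0.06% | 2.5% |

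On the primary (q = f) at VE 27% the same vaccine passes 0.12% of the time at f = 2% and 0.02% at f = 4%. For respiratory illness, assuming f = 3% and q = 20/30%, it passes 93/99.9% at VE 27%, 65/98% at VE 40% and 21/87% at VE 50%.

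**Without assuming a comparator VE.** A vaccine exactly at the primary margin (RRflu = 1.2) meets the ILI rule 25/71/93/99% of the time at f = 2% and 6/47/83/97% at f = 4%, against 2.5% on the primary.

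**Both rules together.** Simulating influenza and other ILI jointly with the score test, an inert vaccine meets both rules about 0.1% of the time or less at VE 27%. The chance of failing the primary but meeting the ILI rule is therefore almost the same as the VE 27% rows above. At VE 9%, which the same Introduction paragraph gives for H3N2 in the elderly, it meets both 9-10% of the time at f = 2% and 14-16% at f = 4%.

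**The case against.** The plan has a fair defence. SAP 8.3.1 gives the secondary endpoints a supportive role without type I error control, and exploratory endpoint 2 ranks lower still. Both endpoints are openly defined as regardless of laboratory result, and ruling out a 20% excess of all ILI is a legitimate question about total symptomatic burden. The chances above run from about 0 to 99.9% according to rates that the documents do not give. The 27% is one season's figure and not specific to this comparator. At VE 50% with 4% influenza the problem almost disappears.

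Most of this stands and keeps the point small. It does not remove it. SAP 8.3.1 concerns multiplicity; it neither ties these tests to the primary nor withdraws the planned conclusion, and it does not cover the exploratory endpoint. Supportive evidence should also separate a working vaccine from an inert one. At 2% influenza, 10% ILI and VE 27%, the vaccine as planned (RRflu 0.8) meets the ILI rule 97% of the time and an inert one 50%, a ratio of 1.9. On the primary the ratio is over 600.

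A reader might infer that the all-cause tests are invalid or that the primary conclusion is compromised. Neither follows: the test is valid for the all-cause ratio, and the primary analysis does not use it. The 9% superiority threshold is not at fault either, because dilution makes it harder to reach.

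**Conclusion.** The point holds as a minor one about interpretation. The -20% rule is carried to two endpoints for which it was neither justified nor powered, and there the 1.2 margin can exceed the comparator's whole effect. Whether it does depends on the influenza share and comparator VE, neither of which is given for these endpoints. At 2% influenza it does so once total ILI passes 3.7% (VE 27%) to 10% (VE 50%). The calculations assume equal non-influenza illness in both arms and 10% dropout. The primary decision, its error rate and the VE estimates are unchanged.

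Two stronger readings go too far. One is that the margin must exceed the comparator's effect; with a high influenza share or high VE it does not. The other is that requiring the primary as well always guards against an inert vaccine. That holds at VE of about 27% or more. At 9% the comparator's whole effect is RR 1/0.91 = 1.10, inside 1.2 even for confirmed influenza, so there the margin is loose for the primary too and dilution is not the only weakness.

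**What to change.** In SAP 8.3 and 8.4, limit non-inferiority and superiority conclusions to the RT-PCR-confirmed endpoints. For secondary endpoint 4 and exploratory endpoint 2, report attack rates, VE and 95% CI descriptively. List the departure from protocol 12.3.2 and 12.3.3 in SAP 12, which already records four changes. If protocol 17.1 is read as requiring a formal amendment for this, include it in the next one.

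The cost is a few sentences. VE and its interval are already planned, so no new data or programs are needed, and readers can still compare the interval with -20% themselves. The sponsor gives up protocol-specified formal statements on two unadjusted, non-primary endpoints.
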